### **Study Stopping Rules**

Study enrollment will be put on temporary hold and expedited reports will be prepared and reported to the DSMB for an ad hoc meeting if any the following occur: 1) Severe GI intolerance to chloroquine 2) Anaphylactic/high risk reaction to chloroquine 3) Symptomatic COVID-19 infection 4) QT prolongation and torsades de point that, in the opinion of the investigator, are clinically significant and indicate an unacceptable risk for the patient's participation in the study. 2) The occurrence of NCI-CTCAE Grade 3 or higher adverse events (including serious adverse events) that are related to study drug in 1 of the first 6 subjects, 2 of the first 23 or 3 of the first 45 or 5 subjects at any time. (It is estimated that the prevalence of Grade 3 or higher adverse events in the placebo group will be about 1 percent.), 3) At the request of the DSMB. The DSMB may only stop the trial for safety concerns. DSMB members: [name], [name], [name]. The DSMB will meet monthly to evaluate any safety and unforeseen protocol issues.

### **ECG**

Per the Food and Drug Administration Emergency Use Authorization guidelines with respect to chloroquine, a single 12-lead standard ECG will be obtained locally at Visit 1 and read by a qualified physician (the investigator or qualified designee) at the site to determine whether the patient meets entry criteria. However if the subject had received an ECG test within the past 12 months and no abnormalities were found, the ECG does not have to be obtained. An ECG test will be administered at the end of the study. Electrocardiograms may be obtained at additional times, when deemed clinically necessary. If the patient presents with unanticipated ECG findings, they will be referred to a cardiology specialist immediately. Patients with QTc between 460-500 msec will be reviewed with a Cardiologist before initiating treatment. Randomization: Randomization to the study drug versus the placebo will be performed in a 1:1 fashion. Simple randomization without blocking or stratification will be followed, with treatment allocation according to a pre-specified computer-generated randomization list provided to the research pharmacy. Blinding: Randomization will be accomplished by the Research Pharmacy, which will provide the study drug and the placebo in identical pill bottles. This will ensure double-blinding to both participants and the study team. In case of an emergency, the investigator has the sole responsibility for determining if unblinding of a patient's treatment assignment is warranted.

Patient safety must always be the first consideration in making such a determination. If the investigator decides that unblinding is warranted, the investigator should make every effort to contact the Research Pharmacy prior to unblinding a patient's treatment assignment unless this could delay emergency treatment of the patient. All calls resulting in an unblinding event are recorded and reported to the IRB. If an investigator, site personnel performing assessments, or patient is unblinded, the patient must be discontinued from the study unless there are ethical reasons to have the patient remain in the study.

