**Secondary Endpoints:** 1. Decrease by 67% in number of sero-conversions in at risk healthcare workers. 2. Percent of patients with adverse events NCI-CTCAE Grade 3 or higher. 3. Percent of patients with GI intolerance.

**Inclusion Criteria:** 1) Age  $\geq$ 18 years, 2) Employment by New York Presbyterian Hospital 3) Clear assignment to areas of the hospital that involve patient contact and possible exposures for at least 2 days a week  $\geq$  8 hours a day

**Exclusion Criteria:** 1) Individuals who are taking CQ for other indications 2) New use of NSAIDs 3) High risk background medications not limited to immunosuppressive regimens, steroids, anti-B cell therapies, anti-cytokine therapies, chemotherapies, JAK-inhibitors 4) Individuals with a history of retinopathy that would contraindicate the use of CQ 5) Known allergy to CQ or chloroquine 6) Known QT prolongation and torsades de point 7) Have screening electrocardiogram (ECG) abnormalities that, in the opinion of the investigator, are clinically significant and indicate an unacceptable risk for the patient's participation in the study. 8) Any individual with QTc over 500 msec will be excluded. 8) Individuals who have history of any cardiac disease. 9) Individuals with history of renal disease 10) Individuals who are taking any QT prolonging meds such as but limited to: • Antipsychotics: Haloperidol, Ziprasidone, Quetiapine, Thioridazine, Olanzapine, Risperidone • Antiarrhythmics: Amiodarone, Sotalol, Dofetilide, Procainamide, Quinidine, Flecainide • Antibiotics: Macrolides, Fluoroquinolones • Antidepressants: Amitriptyline, Imipramine, Citalopram, • Others: Methadone, Sumatriptan, Ondansetron, Cisapride

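### The Visit 1 ECG waiver does not require the site to hold or read a QTc, so the cardiology review required at 460-500 msec could be missed before the first dose

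*Combined protocol and SAP*

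**What the plan says.** The default in the ECG section of the combined protocol and SAP is that "a single 12-lead standard ECG will be obtained locally at Visit 1", to be "read by a qualified physician (the investigator or qualified designee) at the site to determine whether the patient meets entry criteria". The sentence after it lifts this requirement when the subject "had received an ECG test within the past 12 months and no abnormalities were found, the ECG does not have to be obtained".

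Three entry rules depend on an ECG:

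- ECG section: "Patients with QTc between 460-500 msec will be reviewed with a Cardiologist before initiating treatment".
- Exclusion Criteria, the QTc limit: "Any individual with QTc over 500 msec will be excluded".
- Exclusion Criteria, item 7, which applies to those who "Have screening electrocardiogram (ECG) abnormalities that, in the opinion of the investigator, are clinically significant" and carry unacceptable risk. It gives no numeric limit.

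The only other scheduled ECG is at the end of the study. Further ECGs are optional, on clinical need. Under Treatment Description, dosing starts at 500 mg of CQ daily for a week and then becomes weekly.

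**The concern.** The plan sets a numeric trigger, 460 msec, for a specialist opinion before the first dose. The waiver removes the only scheduled pre-dose source of that number and does not require a substitute. It does not define an ECG free of abnormalities by QTc, and it does not say who must have made that judgement. An earlier reader, working for another purpose, had no reason to apply this trial's 460 msec limit.

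What is at stake is a missed consultation. QTc of 460-500 msec is not an exclusion, so a person in that band is eligible. The plan nevertheless requires a cardiologist's review first, in workers who are taking the drug for prevention.

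**Working it through.** The plan states no figure on this point, so there is none to reproduce. The check compares the default with the waiver, looks for another pre-dose source of QTc, and then sizes the gap.

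**1. Default against waiver (ECG section).**

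| Element | Default Visit 1 ECG | Waiver |
|---|---|---|
| Type of test | 12-lead | an ECG test, type not stated |
| Timing | Visit 1 | any time in the past 12 months |
| Reader | qualified physician at the site | not stated |
| Tracing or report held by the site | follows from the site reading | not required |
| QTc value | can be read from the tracing | not required |

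**2. Other pre-dose sources of QTc.**

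- The exclusions for known QT prolongation, cardiac disease and renal disease, and for "Individuals who are taking any QT prolonging meds", lower the risk. They work from history and medication and produce no QTc.
- Cardiology referral for unexpected ECG findings needs an ECG to have been done.
- The Study Stopping Rules list "QT prolongation and torsades de point that, in the opinion of the investigator, are clinically significant". That trigger, like the monthly DSMB meetings, acts after the event.
- The end-of-study ECG comes after dosing.

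None of these gives the site a QTc before the first dose.

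**3. Size.** From Sample size, N = 2 × 175 = 350. The documents give none of the other inputs:

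- w, the share of participants who are waived (assumed)
- p, the share of waived participants with QTc 460-500 msec (assumed)
- u, the share of those whose QTc the site does not have (unknown, between 0 and 1)

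Expected number starting study treatment without the review = N × w × p × u. Setting u = 1 supposes that no waived person's QTc is on hand, so each result is a ceiling for its w and p:

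| w | p | Ceiling, both arms | Ceiling, CQ arm (half) |
|---|---|---|---|
| 0.10 | 0.001 | 350 × 0.10 × 0.001 = 0.035 | 0.02 |
| 0.10 | 0.01 | 350 × 0.10 × 0.01 = 0.35 | 0.18 |
| 0.50 | 0.05 | 350 × 0.50 × 0.05 = 8.75 | 4.4 |
| 1.00 | 0.05 | 350 × 1.00 × 0.05 = 17.5 | 8.75 |

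One such participant is expected when w × p × u = 1/350 = 0.29%. With u = 1 this needs p = 0.00286/0.10 = 2.9% at w = 0.10, or 0.00286/0.50 = 0.57% at w = 0.50. A smaller u raises the required p in proportion: at u = 0.5 the values double to 5.7% and 1.14%.

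The ceilings span a factor of 17.5/0.035 = 500. They show scale only and are not estimates. The relevant p is among people whose earlier ECG was called normal and who passed the exclusions above. The documents give no figure for that group.

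**The case against.** The strongest reply is that the waiver drops a repeat ECG and leaves the QTc rules in place. Neither numeric rule is tied to the Visit 1 tracing. Read together, the rules oblige the site to know the QTc from the old ECG or a new one, and the site needs some basis for saying that nothing abnormal was found. A QTc of 460-500 msec could itself be read as an abnormality, which would make the waiver unavailable.

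Part of this stands. The rules do still apply to waived participants, and many sites would look at the earlier report. But the plan does not say that they must. Even if 460-500 msec counts as abnormal, the site needs the value to know that the waiver is closed. A site could follow the waiver as written and hold no QTc.

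It is also fair to say that people in the band are eligible, that the plan attaches no stated outcome to the consultation, and that about half would receive placebo. These points limit the weight of the concern without closing the gap.

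Three stronger readings are tempting, and the documents do not support them:

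- A reader might infer that people with QTc over 500 msec will be enrolled. The waiver needs an ECG with nothing abnormal found, and a tracing with QTc that long would hardly be described so. The exposure is formal.
- A reader might infer that waived participants never have a QTc on hand. The plan fails to require one, but the site may well hold the report.
- A reader might infer that the efficacy comparison is affected. Nothing in the primary analysis uses the QTc, and the waiver is applied at screening in both arms alike.

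**Conclusion.** The point holds for the 460-500 msec band. As written, the waiver lets a participant begin treatment without the site having the number that the plan's own pre-treatment review depends on, and no other scheduled procedure supplies it.

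The number affected cannot be computed from the documents and is probably small. Under the assumed 10-50% waived and 1-5% in the band, the ceiling is about 0.4 to 9 of 350, half of them on CQ. It is lower to the extent that sites already hold the QTc. Those assumed shares are not limits, and other values give the wider range shown in the working.

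This is a cheap safety improvement. It does not put the trial's conclusions in question. Confidence is medium, because a reasonable site could already read the rules as requiring the value.

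**What to change.** Keep the waiver and make it conditional: it applies only if the earlier 12-lead tracing, or a report stating the QTc, is obtained and a qualified site physician confirms QTc below 460 msec. Otherwise do the default Visit 1 ECG and apply the existing 460-500 and over-500 msec rules.

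The cost is a sentence or two of amendment wording, retrieval of an existing record, and some additional ECGs of the kind that the plan already treats as the default. The most that could be needed is one per waived participant: 350 × 0.10 = 35 to 350 × 0.50 = 175 at the assumed shares, and 350 if everyone were waived. No new procedure or staff is needed.

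The change closes the missing-value gap only. It would not detect a silent change in QTc since the earlier ECG, which only a current tracing can show.

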NCT04349371

Title: Chloroquine (CQ) prophylaxis for Health Care Workers at risk for COVID

Short title: Saved by CQ

Clinical Phase: II

PI: [name] MPH

Co-investigator: [name] MPH

Protocol Version: 3.0 (IRB approved 11/09/2020)

**Primary Objective:** The primary objective is to determine the clinical efficacy of CQ in health care workers with moderate to high risk of exposure to COVID-19 in preventing symptomatic COVID-19 infections.

**Secondary Objectives:** Secondary endpoints will explore the efficacy of CQ in preventing any infection as defined by seroconversion to positive anti-COVID antibody status.

**Study Design:** Double blind, placebo controlled, randomized study of CQ in health care workers with risk of COVID exposure. The primary objective is to determine the clinical efficacy of CQ in health care workers with moderate to high risk of exposure to COVID-19 in preventing symptomatic COVID-19 infections. Safety assessments include AEs, vital signs, ECGs, and physical examinations.

Stratification will be based and levels of exposure: -moderate risk: defined by patient facing work in outpatient/in-house clinic at least 2 days/week -high risk: ICU/ER/procedure rooms with aerosolized particles and high risk of contamination Stratification based on age: -Under 50 years of age -Older than 50 years of age

**Sample size:** 175 patients/group. Sample size based on a projection that 15% of healthcare workers will develop symptomatic COVID-19 illness and an anticipated 67% reduction in rate (i.e. 5%) among those treated with CQ. 175 patients per group, allowing for a 10% dropout rate, will permit detection of a difference of this magnitude or greater for the primary endpoint, assuming a two-tailed alpha and 80% power. The trial is not powered on any secondary outcomes or interim analyses.

**Study Duration:** -1 month accrual of patients with treatment duration of 2-3 months or until exposure levels become negligible - 2 month follow up visit, 3 month follow up visit

**Treatment Description:** 3 Patients will receive CQ 500 mg every day for one week, then 500 mg weekly for the duration of the exposure. A dose of 250 mg daily will be allowed for severe GI intolerance.

**Primary Endpoint:** Decrease by 67% in number of symptomatic illness in at risk healthcare workers; a decrease in symptomatic COVID infections from 15% to 5% in the treatment arm.

**Co-primary Endpoint:** Decrease by 70% in number of severe illness in at risk healthcare workers.

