### **Statistical analysis**

Summary statistics for outcomes and predictor variables will be calculated, with comparisons made using Student's t-test and Wilcoxon rank-sum test for normally and non-normally distributed continuous variables, respectively. Counts and percentages will be calculated for categorical variables and compared using  $\chi^2$  or Fisher's exact test as appropriate. COVID disease status will be ascertained based on medical records review for severe hospitalized patients, self-reported history of viral illness with serological confirmation of anti-COVID status, and anti-COVID antibody status. The association between CQ and disease will be explored. Efficacy analyses included all the patients who underwent randomization and who received at least one dose of CQ or placebo (modified intention-to-treat population). The primary end point, the percentage of patients with COVID infection at study end, will be compared in the CQ group and in the placebo group with the use of a stratified Cochran–Mantel–Haenszel test, with strata corresponding to the stratification factors (age and exposure levels). To isolate the association between CQ and possible confounders we will define as those variables associated with both the outcome and the independent variable (CQ). Statistical calculations will be performed using STATA version 12. A two-tailed  $\alpha$  of 0.05 was defined as the level of statistical significance for all tests.

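### By default an unblinded participant leaves the study, not just blinded treatment, and the plan makes no provision for collecting the outcomes that the modified ITT analysis still needs.

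*Combined protocol and SAP*

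**What the plan says.** The rule is in the blinding text of the ECG section. If an investigator, site staff performing assessments, or the participant becomes unblinded, "the patient must be discontinued from the study unless there are ethical reasons to have the patient remain in the study". What ends is participation in the study, not only study drug or blinded assessment. The ethical reasons are not defined.

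The same section describes one route to a deliberate code break: "In case of an emergency, the investigator has the sole responsibility for determining if unblinding of a patient's treatment assignment is warranted". Calls that lead to unblinding are recorded and reported to the IRB.

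The Statistical analysis section defines the efficacy set as all randomised participants who "received at least one dose of CQ or placebo (modified intention-to-treat population"). It assesses the primary endpoint at study end. COVID status comes from medical records for severe hospitalised patients, and otherwise from self-reported illness confirmed by serology, or from antibody status. Neither section says whether outcomes are collected after discontinuation, and there is no rule for missing outcomes.

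**The concern.** An analysis based on everyone dosed needs an outcome for everyone dosed. Here a post-randomisation event, the code break, by default ends participation before the time at which the endpoint is assessed. Because deliberate code breaks are for emergencies, the participants removed may differ from the rest in illness or toxicity. The missing outcomes then cannot be assumed to be missing at random.

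Four kinds of data are exposed: final serology (needed for the seroconversion endpoint and to confirm non-hospitalised illness), non-hospitalised illness itself, adverse events after the code break, and the end-of-study ECG. At the design rates the trial expects few cases, so each lost case counts. If the share of cases lost differs between arms, the estimated effect is biased. If it is the same, the main cost is power.

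**Working it through.** **1. Inputs.** From the sample-size text of the synopsis: "15% of healthcare workers will develop symptomatic COVID-19 illness"; "an anticipated 67% reduction in rate (i.e. 5%) among those treated with CQ"; "175 patients per group, allowing for a 10% dropout rate"; "assuming a two-tailed alpha and 80% power". The significance level is in the Statistical analysis section: a two-tailed α "of 0.05 was defined as the level of statistical significance for all tests". Allocation is 1:1 (ECG section). No unblinding rate is given, so every loss percentage below is an assumption.

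**2. The plan's own figure.** Without continuity correction, with mean rate 0.10:

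n = [1.96·√(2·0.10·0.90) + 0.842·√(0.15·0.85 + 0.05·0.95)]² / 0.10² ≈ 140.1, so 141 per arm.

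With continuity correction: n = (140.1/4)·[1 + √(1 + 4/(140.1·0.10))]² ≈ 159.5, so 160 per arm.

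Allowing for 10% dropout: 160/0.9 = 178, or 160·1.1 = 176. The stated 175 is reproduced to within 3%.

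**3. Evaluable participants and expected cases.** 175·0.9 = 157.5 per arm. Expected cases are 157.5·0.15 = 23.6 on placebo and 157.5·0.05 = 7.9 on CQ. Losing 20% of placebo cases means losing about 4.7 people.

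**4. Loss model.** Let u be the share of an arm's cases whose outcome is lost through the rule, and p the true rate. There are two conventions, because the plan does not say which applies:

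- Lost cases leave numerator and denominator: observed rate = p(1−u)/(1−pu).
- Lost cases stay in the set as non-events: observed rate = p(1−u).

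*First convention* (157 per arm, exact enumeration of two binomials, Pearson chi-square at two-sided 0.05):

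| Cases lost, placebo / CQ | Observed rates | Risk ratio | Power |
|---|---|---|---|
| 0 / 0 | 15.0% / 5.0% | 0.33 | 86% |
| 10% / 10% | 0.135/0.985 = 13.7% / 0.045/0.995 = 4.5% | 0.33 | 83% |
| 20% / 20% | 0.12/0.97 = 12.4% / 0.04/0.99 = 4.0% | 0.33 | 78% |
| 20% / 0 | 0.12/0.97 = 12.4% / 5.0% | 0.40 | 66% |

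*Second convention* (157.5 per arm, normal approximation, 84.4% power with no loss):

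| Cases lost, placebo / CQ | Observed rates | Risk ratio | Power |
|---|---|---|---|
| 10% / 10% | 13.5% / 4.5% | 0.33 | 80.0% |
| 20% / 20% | 12.0% / 4.0% | 0.33 | 74.7% |
| 20% / 0 | 12.0% / 5.0% | 0.42 | 60.6% |
| 0 / 20% | 15.0% / 4.0% | 0.27 | not comparable: the effect is overstated |

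**5. Reading.** Equal loss costs a few points of power and leaves the risk ratio essentially unchanged. Unequal loss moves it in either direction, according to which arm loses more cases.

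**The case against.** The strongest reply is that little outcome information need be lost. An event that prompts a code break has already happened and is normally known to the study. A Grade 3 or higher event that led to unblinding already counts, because that endpoint is the percentage of patients with such an event. Severe hospitalised cases are ascertained from medical records, which needs no further visit. The rule has an exception, and it also covers unblinding of an investigator or assessor, which need not reflect the participant's condition. The decision to unblind is made before the arm is known, so equal loss is the natural base case.

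Most of this stands, and it rules out several stronger readings that a reader might infer:

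- *That the rule contradicts the modified ITT definition.* It does not. Membership is fixed by randomisation and one dose. A discontinued participant stays in the set but may have no study-end outcome.
- *That the sickest participants and their serious events disappear because they happened.* The documents do not show this: the triggering event normally precedes the code break and is known.
- *That the severe-illness co-primary endpoint is the most exposed.* Records review makes it better protected than non-hospitalised illness awaiting serology.
- *That the rule inflates type I error.* With 15% in both arms, losing 20% of CQ cases against 0 to 5% of placebo cases would give a risk ratio of 0.82 to 0.86 and a type I error of 8 to 10%. That comes entirely from the assumed imbalance; equal loss leaves it at 5%.

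What the reply does not remove is the default itself. Following the sentence as written ends participation before study end, the exception leaves retention to undefined discretion, and nothing provides for the serology, later safety data or ECG still due.

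**Conclusion.** The point holds as a flaw in the follow-up rule, not as a demonstrated bias. Removal from the study is the default after unblinding, it can be related to illness or toxicity, and the analysis set still needs outcomes that nothing in the plan provides for collecting.

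The size cannot be determined from the documents. The loss percentages in the tables are illustrative, and a 20% loss of all cases through code breaks would be high, since most symptomatic illness need not be an emergency. At 10% equal loss the cost is about 3 to 4 points of power. A distorted effect estimate requires loss that differs by arm, for which the documents give no figure. This is a cheap improvement; the sample size need not change.

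**What to change.** Replace the discontinuation sentence in the ECG section with:

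*Unblinding alone does not end study participation: unless consent is withdrawn, unblinded participants complete all scheduled outcome and safety assessments, including final serology and ECG, and their outcomes are used in the modified ITT analysis.*

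In the Statistical analysis section, add a sensitivity analysis for illness self-reported after unblinding, and state how outcomes that remain missing are handled. Whether study drug continues after unblinding is a separate clinical decision left to the sponsor.

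The cost is one protocol sentence and a short SAP addition, with no new visits. The small downside is that a few self-reported outcomes will be collected unblinded. Serology is an objective measure and much less affected, and the sensitivity analysis shows how far the self-reports matter.
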